9.4.3 ANALYSIS OF THE SECONDARY ENDPOINT(S)

For **Aim 2**, we will calculate rates of recruitment, retention and compliance. No hypothesis tests will be performed. However, correlates to these metrics will be assessed. For each of the outcome measures the between session analysis will allow us to calculate test-retest reliability. The use of correlations will allow us to compute criterion and predictive validity.

Study retention will be defined as a subject who attends each of the biomechanical testing session (baseline, immediately following intervention (intervention)/6 weeks after baseline (control), and then 6 weeks after training (intervention) or 12 week after the baseline (control). Proportion retention will be computed by dividing the number of retained subjects at the end of the intervention by the total number of patients randomized into the study. Compliance with the intervention will be defined as a subject who attends at least 80% of the biofeedback training sessions during the six weeks of the intervention. Proportion adherence will be computed by dividing the number of sessions attended by the total number training sessions (number of training sessions n=12).

9.4.4 SAFETY ANALYSES

Monthly reports will describe target and actual enrollment by site and in aggregate, individuals screened with reasons for screen failure, and enrollment status (enrolled, active, completed, discontinued treatment, and lost to follow-up). Monthly reports will also list or summarize AEs and SAEs. Administrative reports will list the forms completed, entered, and missing, and/or erroneous data and forms. The NIAMS has requested a monthly study update to be provided on the fifth of every month by the study PI. Reports to the Safety Officer (SO) will be completed biannually throughout the study and will be submitted by the study PI to KAI based on a schedule that will be on when the first subject is enrolled into the study.

9.4.5 BASELINE DESCRIPTIVE STATISTICS

Not applicable – study will be block randomized in order to decrease the potential for differences in baseline characteristics between the two study groups (Intervention and Control).

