4.1 OVERALL DESIGN

Aim 1: Determine the impact of a biofeedback training program on decreasing asymmetrical vertical ground reaction forces, frontal plane knee range of motion and the peak knee extension moment, known risk factors for secondary ACL injuries.
We will test the hypothesis that our biofeedback program will decrease the risk of secondary ACL injury by improving loading and movement symmetry during the dynamic task of landing from a jump 6 weeks post intervention.

Aim 2: To demonstrate our ability to recruit, retain and determine patient compliance in completing a biofeedback retraining program. We will demonstrate our ability to recruit 40 ACL reconstructed patients and assess study retention and compliance.

Overview: The goal of this single site, pilot randomized clinical trial is to determine the impact of an innovative biofeedback training program on decreasing surrogate measures of secondary ACL injury risk in adolescent athletes. Movement and loading symmetry will be assessed using the limb symmetry index ($LSI = \frac{ABS[Surgical] - ABS[Nonsurgical]}{0.5(ABS[Surgical] + ABS[Nonsurgical])} * 100$)^{2,3,7,34} prior to (baseline) and at two time points following (immediately following training (efficacy), and 6 weeks after (durability)) the biofeedback training program (**Aim 1; Figure 1**).

40 adolescent ACL patients (20 control, 20 intervention) will be recruited. Subjects will be block randomized into either the control arm or the intervention arm at baseline. All intervention subjects will complete an in-person (no home exercises) biofeedback retraining program for 6 weeks (2 times per week) with a focus on improving both load and movement symmetry through the use of tactile and visual feedback (**Figure 1**), which has been reported to be an effective biofeedback intervention²⁶. Finally, this study will demonstrate our ability to recruit subjects, engage them in the novel biofeedback program, and retain them until study completion. The outcomes from **Aim 2** will inform future study designs.

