6.3 MEASURES TO MINIMIZE BIAS: RANDOMIZATION AND BLINDING

This will be a randomized controlled trial (see figure below).

Participating patients will be randomized using a 1:1 between the Intervention vs. Control arms.

Participants will be equally allocated between the two groups, with randomization stratified according to gender, age and activity level to ensure that the groups are balanced in these respects. All participants in the study will continue with any other usual medical care they receive for their ACL reconstruction.

Eligible participants will be randomized following the first biomechanical assessment (during which informed consent is obtained). After this baseline biomechanical assessment, participants will be scheduled for his/her first study visit (biofeedback intervention or control in-person education session) at this time each participant will be informed about the research arm to which they have been assigned. The Research Assistant will call participants within 24-48 hours of each appointment to remind them of their appointment day and time as well as answer any questions.

Randomization will be based on a computer generated sequence maintained by the project statistician. The Research Assistant or Principle Investigator will obtain the randomization status from the statistician.

Participant randomization assignments will be entered and stored in a password protected, study specific database maintained by the research assistant and verified by the study statistician.

As this is an open trial, therefore, participant unblinding procedures are not necessary.

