9 STATISTICAL CONSIDERATIONS

9.1 STATISTICAL HYPOTHESES

All statistical analysis will be completed under the direction of [name]. Depending on the outcome, change (completion-baseline), or the value at completion will be assessed, and the statistical significance of the group differences can be assessed by a t-test or the non-parametric equivalent (2-sample Wilcoxon). Standardized differences will be calculated for the purposes of powering the subsequent clinical trial.

- **Primary Efficacy Endpoint(s):**
We will test the hypothesis that our biofeedback program will decrease the risk of secondary ACL injury by improving loading and movement symmetry (knee extension moment asymmetry) during the dynamic task of landing from a jump 6 weeks post intervention.

Movement and loading symmetry will be assessed using the limb symmetry index ($LSI = \frac{ABS[Surgical] - ABS[Nonsurgical]}{0.5(ABS[Surgical] + ABS[Nonsurgical])} * 100$)^{2,3,7,34} prior to (baseline) and at two time points following (immediately following training (efficacy), and 6 weeks after (durability)) the biofeedback training program.

- **Secondary Efficacy Endpoint(s):**
No hypothesis testing will be completed for the secondary endpoint as this is a pilot clinical trial and will be used to determine the best procedures to following when planning a subsequent multi-center clinical trial. Therefore, we will demonstrate our ability to recruit 40 ACL reconstructed patients and assess study retention and compliance.

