9.3 POPULATIONS FOR ANALYSES

The following populations will be included in the statistical analysis:

- Modified Intention-to-Treat Analysis Dataset (participants who completed at least 50% of the intervention visits in the Biofeedback Arm of the study and who attended at least one of the post-intervention assessment visits)
- Safety Analysis Dataset: defines the subset of participants for whom safety analyses will be conducted (participants who completed at least intervention visit)
- Per-Protocol Analysis Dataset: defines a subset of the participants in the full analysis (ITT) set who complied with the protocol sufficiently to ensure that these data would be likely to represent the effects of study intervention according to the underlying scientific model (participants who completed at least 80% of the study intervention visits)
- Other Datasets that may be used for sensitivity analyses

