9.4.7 SUB-GROUP ANALYSES

Due to the pilot nature of this clinical trial we will not be performing any subgroup analyses. However, in order to better understand the outcomes and in an attempt to plan for a future multi-center trial, we will explore possible confounders such as age, time from surgery, time in rehabilitation, concomitant meniscal pathology, sex, and the initial injury mechanism. This information could allow for program modifications and/or determine if certain baseline characteristics need to be achieved prior to starting the biofeedback program.

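### No by-arm baseline table is planned and the between-arm test has no baseline covariate, although neither blocking nor the three strata act on the baseline knee extension moment index

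*Combined protocol and SAP*

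**What the plan says.** All references are to the combined protocol and SAP.

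- **Baseline description.** Section 9.4.5 answers its own heading with not applicable. The only reason it gives is that the "study will be block randomized in order to decrease the potential for differences in baseline characteristics between the two study groups".
- **Randomisation.** Section 4.1 states "40 adolescent ACL patients (20 control, 20 intervention) will be recruited" and "Subjects will be block randomized into either the control arm or the intervention arm at baseline". Section 6.3 adds "randomization stratified according to gender, age and activity level to ensure that the groups are balanced in these respects", at a 1:1 ratio. Block size, cut points for age and activity level, and whether the blocks sit within strata are not stated. Section 6.3 places randomisation after the first biomechanical assessment, so the baseline index is measured before allocation.
- **Between-arm test.** Under Section 9.1, "change (completion-baseline), or the value at completion will be assessed", depending on the outcome, by t-test or two-sample Wilcoxon. No baseline covariate is named.
- **Primary model.** Section 9.4.2 specifies a repeated-measures model over the pre-intervention and two post-intervention assessments. It is described as within subject and names no group term.
- **Analysis set.** The modified intention-to-treat set in Section 9.3 is limited to "participants who completed at least 50% of the intervention visits in the Biofeedback Arm of the study" who also attended a post-intervention assessment. No attendance threshold is stated for the control arm.
- **Other uses of baseline data.** Section 9.4.1 gives a general rule for descriptive summaries. In Section 9.4.7, "we will explore possible confounders such as age, time from surgery, time in rehabilitation", meniscal pathology, sex and injury mechanism. Section 10.1.11 plans papers that describe the sample at baseline. None of these commits to a display by arm.

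**The concern.** The reason in Section 9.4.5 does not support its conclusion. Permuted blocks control how many patients enter each arm, not which patients. Stratification controls the factors that define the strata and little else. The covariate most likely to predict the outcome is the baseline value of the outcome itself, and it is not a stratum.

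The analysed groups also need not be the randomised groups. The modified intention-to-treat set applies an attendance filter in one arm after randomisation, and Section 7.2 replaces participants who start the intervention and then withdraw. Even perfect balance at randomisation would not guarantee balance in that set, and a baseline table by analysis set is the direct way to look.

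The stake is the estimate more than the p-value. Section 9.1 says standardised differences from this pilot will be used to power the next trial. An unadjusted shift from baseline imbalance goes straight into that number, and without a by-arm table a reader cannot judge its size.

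**Working it through.** **Plan's own figure.** The plan gives no figure on baseline balance. Its design calculation for the primary measure (Section 9.2, Table 4) reproduces. SD = sqrt((0.9² + 0.5²)/2) = 0.728 and d = (3.7 − 2.4)/0.728 = 1.79. A two-sample t-test at two-sided 0.05 and 80% power needs 6.05 per group, rounded up to the stated 7 (14 overall). This point does not change it.

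**Inputs.** 20 per arm (Section 4.1). 15 per arm, from the Section 9.2 goal of retaining 30, assuming an equal split and random loss.

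**1. What blocking and stratification do.** Simulation of 20,000 trials of 40 patients. Block size 4 and three binary factors, each present in half of patients, are assumptions.
- Plain blocks: arm sizes are exactly equal, yet a binary factor differs between arms by 20 percentage points or more in about 27% of trials. The exact hypergeometric figure is 34% when exactly 20 of 40 have the factor.
- Blocks within strata: the same imbalance in a stratification factor falls to about 0.3%.
- A continuous covariate outside the strata differs by more than 0.5 SD in 11.5% of trials with plain blocks and 11.8% with stratified blocks. Stratifying on other, unrelated factors gives it no protection.

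**2. One unstratified covariate.** The standardised difference has SE = sqrt(2/n), and P(|difference| > 0.5 SD) = 2[1 − Φ(0.5/SE)].
- n = 20: SE = 0.316, P = 0.114.
- n = 15: SE = 0.365, P = 0.171.

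**3. At least one of several.** Section 9.4.7 names six factors. Age and sex are strata, which leaves four: time from surgery, time in rehabilitation, meniscal pathology and injury mechanism. If they are independent, P = 1 − (1 − p)^4.
- n = 20: 1 − 0.886^4 = 0.38.
- n = 15: 1 − 0.829^4 = 0.53.

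The two time variables probably overlap heavily. Counting them as one gives 1 − (1 − p)^3 = 0.30 and 0.43. So 38% and 53% are upper figures.

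**4. Effect of a 0.5 SD imbalance in the baseline index.** Let ρ be the baseline-outcome correlation, with equal SDs at both times. The documents give no ρ; 0.5 to 0.7 is assumed.
- Completion value: shift = 0.5ρ = 0.25 (ρ = 0.5) to 0.35 SD (ρ = 0.7), favouring the arm that started more symmetric.
- Change score: shift = 0.5(1 − ρ) = 0.25 (ρ = 0.5) to 0.15 SD (ρ = 0.7), in the opposite direction.
- Baseline-adjusted: the expected shift is zero under a linear relation.

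**5. Precision.** Variance factors are 1 for completion value, 2(1 − ρ) for change and 1 − ρ² for the adjusted comparison.

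| ρ | Change | Adjusted | Cut vs completion | Cut vs change |
|---|---|---|---|---|
| 0.5 | 1.00 | 0.75 | 25% | 25% |
| 0.7 | 0.60 | 0.51 | 49% | 1 − 0.51/0.60 = 15% |

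**The case against.** **The design does address patient characteristics.** A reader of Section 9.4.5 alone might infer that allocation ignores them. Section 6.3 does not support that: gender, age and activity level are strata, and step 1 shows how effective this can be. For the same reason it would be wrong to count all six Section 9.4.7 factors as unprotected. What remains is that the strata omit the baseline index, time from surgery and meniscal pathology.

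**Baseline data would be looked at.** A reader might infer that imbalance would go unseen. That is too strong, given Sections 9.4.1, 9.4.7 and 10.1.11. The accurate statement is that no display by arm or by analysis set is committed to.

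**The analysis uses baseline.** Section 9.4.2 includes the pre-intervention time point, and Section 9.1 allows change from baseline. So it does not follow that a raw baseline difference always passes into the result: it does so in part (0.5ρ) only under the completion-value option. With change scores the residual is regression to the mean, in the other direction. But neither option adjusts for baseline, and the Section 9.4.2 model as written is not a between-arm comparison.

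**Chance imbalance does not invalidate a randomised test.** This is correct for all randomised participants: the t-test already allows for it over repeated trials. The shifts in step 4 apply to a trial in which the imbalance has occurred. The argument does not cover the attendance-filtered set.

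**It is a pilot.** Section 9.4.9 promises a cautionary note on any significant result, and a shift of 0.35 SD is about a fifth of the 1.79 SD used for planning (0.35/1.79 = 0.20). That limits the severity. But the planning effect is a proxy taken from another study's pre-post contrast, and estimates are this trial's stated product.

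**Conclusion.** The point holds in this form: the reason in Section 9.4.5 does not make a baseline table inapplicable, no other section supplies one by arm, and the explicit between-arm test leaves out a baseline measurement that is already in hand.

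For a single unstratified covariate such as the baseline index, the chance of a difference above 0.5 SD is about 11% at 20 per arm and 17% at 15 per arm. For at least one of the four unstratified Section 9.4.7 factors it is at most about 38% and 53%. A 0.5 SD imbalance in the index would move the unadjusted estimate by 0.15 to 0.35 SD, with the direction depending on which of the two permitted outcomes is chosen.

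These figures rest on normal theory, independence for the four-factor figures, random loss at 15 per arm, and the assumed correlation. They measure chance imbalance only. They do not measure selection from the one-arm attendance filter, whose size the documents give no means to estimate, and they do not show that the result will be biased. This is worth correcting before analysis; it does not undermine the trial.

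**What to change.** 1. **Adjust for baseline.** In Section 9.1, specify the between-arm comparison of the knee extension moment index with the baseline index as a covariate, in place of the choice between change and completion value. If the Section 9.4.2 model is to carry this comparison, it should name group and group-by-time terms. The covariate should be fixed in advance and not depend on whether an imbalance is observed.
2. **Replace Section 9.4.5** with a baseline table by arm, without significance tests, for all randomised participants and for each Section 9.3 analysis set. It should show the baseline index, the three strata and the Section 9.4.7 factors.
3. **Reconcile Sections 4.1, 6.3, 9.4.5 and 10.1.11.** State whether blocks are formed within strata, the block size, and the cut points for age and activity level. Align the planned papers on baseline characteristics with the new table.

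The cost is one table and one model term, with no change to sample size. The Schedule of Activities already places demographics, surgical characteristics and the primary outcome at baseline. It marks activity level in weeks 1 to 6 and not at baseline, so the plan should also say where the pre-randomisation value used for stratification is recorded. Adjustment does not cure the one-arm attendance filter, which needs its own correction; the table by analysis set would only show its effect on measured characteristics.

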9.4.6 PLANNED INTERIM ANALYSES

Not applicable

9.4.7 SUB-GROUP ANALYSES

Due to the pilot nature of this clinical trial we will not be performing any subgroup analyses. However, in order to better understand the outcomes and in an attempt to plan for a future multi-center trial, we will explore possible confounders such as age, time from surgery, time in rehabilitation, concomitant meniscal pathology, sex, and the initial injury mechanism. This information could allow for program modifications and/or determine if certain baseline characteristics need to be achieved prior to starting the biofeedback program.

9.4.8 TABULATION OF INDIVIDUAL PARTICIPANT DATA

Individual participant data will be recorded in the study database, however, study results that will be reported will be based on the group aggregate data for each of the study groups.

9.4.9 EXPLORATORY ANALYSES

Over the course of the study secondary outcomes will be examined to determine any mediating effects these variables may have, which could explain differences across time (**Table 3**). Secondary outcomes will be evaluated using exploratory analyses in order to generate hypotheses for future studies. These exploratory analyses will be conducted using linear mixed models.^{23,35,36} We will test both primary and secondary outcomes at an alpha level of 0.05 and will not control for potential Type-I errors due to multiple testing, using Bonferroni or Hochberg criteria,^{8,9,19} due to the pilot nature of this study. If an effect is declared 'significant' we will provide a cautionary note in resulting publication, as to the exploratory nature of the findings.

Table 3: Outcome Measurements

Primary Outcomes
Peak Knee Extension Moment Symmetry
Secondary Outcomes
Peak Vertical Ground Reaction Force Symmetry
Vertical Ground Reaction Force Impulse Symmetry
Frontal Plane Knee Range of Motion
Peak Knee Flexion Angle Symmetry
Peak Knee Flexion Angle
Peak Knee Valgus

10 SUPPORTING DOCUMENTATION AND OPERATIONAL CONSIDERATIONS

10.1 REGULATORY, ETHICAL, AND STUDY OVERSIGHT CONSIDERATIONS

10.1.1 INFORMED CONSENT PROCESS

10.1.1.1 CONSENT/ASSENT AND OTHER INFORMATIONAL DOCUMENTS PROVIDED TO PARTICIPANTS

All patients will be approached by their treating orthopaedic surgeon to inquire about their interest in hearing more about this clinical trial. At that time the clinician will provide the potential participant with a release letter (MOOP Appendix C) that indicates that the patient is clinically ready to participate in this clinical trial. At that time, the potential participant will also be asked to sign the release of information consent (MOOP Appendix B). This signed form will be sent to the study team to indicate the potential participant's interest in learning more about the research project.

Consent forms describing in detail the study intervention, study procedures, and risks are given to the participant and written documentation of informed consent is required prior to starting intervention/administering study intervention. The following consent materials are submitted with this protocol; (1) adult informed consent, (2) Minor ascent, and (3) parental permission.

10.1.1.2 CONSENT PROCEDURES AND DOCUMENTATION

Informed consent is a process that is initiated prior to the individual's agreeing to participate in the study and continues throughout the individual's study participation. Consent forms will be Institutional Review Board (IRB)-approved and the participant will be asked to read and review the document. The investigator will explain the research study to the participant and answer any questions that may arise. A verbal explanation will be provided in terms suited to the participant's comprehension of the purposes, procedures, and potential risks of the study and of their rights as research participants. Participants will have the opportunity to carefully review the written consent form and ask questions prior to signing. The participants should have the opportunity to discuss the study with their family or surrogates or think about it prior to agreeing to participate. The participant will sign the informed consent document prior to any procedures being done specifically for the study. Participants must be informed that participation is voluntary and that they may withdraw from the study at any time, without prejudice. A copy of the informed consent document will be given to the participants for their records. The informed consent process will be conducted and documented in the source document (including the date), and the form signed, before the participant undergoes any study-specific procedures. The rights and welfare of the participants will be protected by emphasizing to them that the quality of their medical care will not be adversely affected if they decline to participate in this study.

